9.2.2 Reporting Procedures for Serious Adverse Events

The investigator is responsible for ensuring that all serious adverse events observed by the investigator or reported by the subject that occur after signing of the informed consent through 30 days after the last day of the dosing interval of investigational product(s) or end of study, whichever is later, are recorded in the subject's medical record and are submitted to Amgen. All serious adverse events must be submitted to Amgen within 24 hours following the investigator's knowledge of the event via the applicable eCRF.

The serious adverse event must be submitted to Amgen within 24 hours following the investigator's knowledge of the event via the applicable eCRF (eg, the Safety Report Form). If the electronic data capture (EDC) system is unavailable to the site staff to report the Serious Adverse Event, the information is to be reported to Amgen via an electronic Serious Adverse Event (eSAE) Contingency Report Form within 24 hours of the investigator's knowledge of the event. See [Appendix B](#) for a sample of the electronic Serious Adverse Event Contingency Report Form. For EDC studies where the first notification of a Serious Adverse Event is reported to Amgen via the eSerious Adverse Event Contingency Report Form, the data must be entered into the EDC system when the system is again available.

The investigator must assess whether the serious adverse event is possibly related to SC IP (evolocumab or placebo) or PO IP (ezetimibe or placebo). This relationship is indicated by a "yes" or "no" response to the question: Is there a reasonable possibility that the event may have been caused by SC IP or PO IP? **Relatedness means that there are facts or reasons to support a relationship between IP and the event.**

The investigator must assess whether the serious adverse event is possibly related to the prefilled AI/Pen or Personal Injector Amgen device used to administer SC IP. The relationship is indicated by a "yes" or "no" response to the question: Is there a reasonable possibility that the event may have been caused by the Amgen device?

The investigator must assess whether the serious adverse event is possibly related to any study-mandated activity or procedure. This relationship is indicated by a "yes" or "no" response to the question: "Is there a reasonable possibility that the event may have been caused by a study activity/procedure"?

The investigator is expected to follow reported serious adverse events until stabilization or reversibility.

New information relating to a previously reported serious adverse event must be submitted to Amgen. All new information for serious adverse events must be sent to Amgen within 24 hours following knowledge of the new information. The investigator may be asked to provide additional follow-up information, which may include a discharge summary or extracts from the medical record. Information provided about the serious adverse event must be consistent with that recorded on the applicable eCRF (eg, Event eCRF).

If a subject is permanently withdrawn from protocol-required therapies because of a serious adverse event, this information must be submitted to Amgen.

To comply with worldwide reporting regulations for serious adverse events, the treatment assignment of subjects who develop serious, unexpected, and related adverse events may be unblinded by Amgen before submission to regulatory authorities. Investigators will receive notification of related serious adverse events reports sent to regulatory authorities in accordance with local requirements.

Amgen will report serious adverse events and/or suspected unexpected serious adverse reactions as required to regulatory authorities, investigators/institutions, and IRBs/IECs in compliance with all reporting requirements according to local regulations and good clinical practice.

The investigator is to notify the appropriate IRB/IEC of serious adverse events occurring at the site and other adverse event reports received from Amgen, in accordance with local procedures and statutes.

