Abbreviation or Term	Definition/Explanation
OLEAS	Open Label Extension Analysis Set
PBO	Placebo
PCI	Percutaneous coronary intervention
PCSK9	Proprotein convertase subtilisin/kexin type 9
PKPD	Pharmacokinetic / pharmacodynamics
PO	Oral administration
Q2W	Q2W is defined as every 2 weeks with a window of \pm 3 days
Q4W	Every 4 weeks, (AMG 145 Background Section)
QD	Each day
QM	QM is defined as every 4 weeks with a window of \pm 7 days
QW	Every week
Randomized	Assignment to treatment group based on computer-generated randomization schedules prepared by Amgen before the start of the study
RAS	Rechallenge Analysis Set
RBC	Red blood cells
RR	Respiratory rate
SBP	Systolic blood pressure
SC	Subcutaneous
SD	Standard deviation
SF-36	Short Form (36) Health Survey
Source Data	Information from an original record or certified a copy of the original record containing patient information for use in clinical research. The information may include, but is not limited to, clinical findings, observations, or other activities in a clinical trial necessary for the reconstruction and evaluation of the trial. Source data are contained in source documents (original records or certified copies). (ICH Guideline (E6)). Examples of source data include Subject ID, Randomization ID, and Stratification Value.
TBL	Total bilirubin
TIA	Transient ischemic attack
Tmax	Time to maximum concentration
TSH	Thyroid stimulating hormone
ULN	Upper limit of normal
VLDL-C	Very low-density lipoprotein cholesterol
WBC	White blood cell

TABLE OF CONTENTS

Protocol Synopsis	3
Study 20140234 Treatment Schema	7
Study Glossary	8
1. OBJECTIVES	15
1.1 Primary	15
1.2 Secondary	15
2. BACKGROUND AND RATIONALE	15
2.1 Disease	15
2.2 Amgen Investigational Product Background	18
2.3 Non-Amgen Medicinal Product Background	19
2.4 Rationale	20
2.5 Clinical Hypotheses	21
3. EXPERIMENTAL PLAN	21
3.1 Study Design	21
3.2 Number of Sites	22
3.3 Number of Subjects	22
3.4 Replacement of Subjects	22
3.5 Estimated Study Duration	22
3.5.1 Study Duration for Subjects	22
3.5.2 End of Study	23
4. SUBJECT ELIGIBILITY	23
4.1 Inclusion and Exclusion Criteria	23
4.1.1 Inclusion Criteria	23
4.1.2 Exclusion Criteria	24
5. SUBJECT ENROLLMENT	27
5.1 Randomization/Treatment Assignment	27
5.2 Site Personnel Access to Individual Treatment Assignments	28
6. TREATMENT PROCEDURES	28
6.1 Classification of Product(s) and/or Medical Device(s)	29
6.2 Investigational Product	29
6.2.1 Amgen Investigational Product Evolocumab (AMG 145)	29

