7. STUDY PROCEDURES

7.1 Schedule of Assessments

Table 1. Schedule of Assessments

Study Day / Timepoint	Screening & Placebo Run-in	D1 Visit	W2 Visit	W4	W6	W8 Visit	W10 Visit	W12 Visit	W24 Visit	W36 Visit	W48 Visit	W52 Visit	W54 ⁱ EOS Phone Call
General Procedures													
Informed consent	X												
Medical history	X												
Vital Signs (sitting BP, HR, RR, Temp)	X	X				X	X	X	X	X	X	X	
Review for AE/SAE/ADE ^a	X	X	X			X	X	X	X	X	X	X	X
Concomitant therapy	X	X	X			X	X	X	X	X	X	X	X
Dietary instruction	X	X	X			X	X	X					
Physical exam	X							X				X	
Body weight, waist circumference	X											X	
Body height	X												
SF-36		X						X					
Randomization		X											
Central Laboratory													
Fasting lipids ^b	X	X	X			X	X	X	X	X	X	X	
ApoA1, ApoB, Lp(a)		X					X	X	X	X	X	X	
PK, PCSK9		X	X				X	X				X	
Chemistry ^c Hematology ^d	X	X				X		X				X	
hsCRP		X						X				X	
HbA1c	X							X				X	
TSH	X												
Biomarkers (blood)		X						X				X	
Anti-evolocumab antibodies		X						X				X	
HCV antibodies	X												
HCV viral load (only HCV positive patients)		X						X				X	
Serum pregnancy; FSH	X							X				X	
Urine pregnancy^e		X	X			X	X	X					
Urinalysis ^f	X	X						X				X	
SC Placebo Run-in	X												
Q2W SC IP on-site		X	X			X	X	X					
Q2W SC IP non-clinic setting ^g				X	X				X	X	X		
Q2W IP Dispensation/Accountability		X	X			X	X	X	X	X	X	X	
QM SC IP on-site		X				X		X					
QM SC IP non-clinic setting ^h				X					X	X	X		
QM IP Dispensation/Accountability		X	X			X		X	X	X	X	X	
PO IP Dispensation/Accountability		X	X			X	X	X					

Footnotes defined on next page of the table

^a **Review for adverse events, serious adverse events, and adverse device effects. Adverse events possibly related to study procedures, adverse device effects, and serious adverse events** are collected **during the screening period** from signing of the ICF through 30 days post last dose of IP or EOS, whichever is later.

^b Fasting lipids: Total cholesterol, HDL-C, LDL-C, Triglycerides, VLDL-C, non-HDL-C.

^c Chemistry: Sodium, Potassium, Chloride, Bicarbonate, Total protein, Albumin, Calcium, Magnesium, Phosphorus, Fasting Glucose, BUN or Urea, Creatinine, Uric acid, Total bilirubin, Direct bilirubin, CK, Alk phos, LDH, AST (SGOT), ALT (SGPT).

^d Hematology: RBC, Hemoglobin, Hematocrit, MCV, MCH, MCHC, RDW, WBC, Platelets

^e Prior to on-site SC IP administration, **female** subjects of childbearing potential should have urine pregnancy test performed.

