3.1 Study Design

This is a phase 3, multicenter, double-blind, randomized, ezetimibe controlled, parallel group study for evolocumab in hypercholesterolemic Japanese subjects unable to tolerate an effective dose of a statin. Subjects who meet all inclusion/exclusion criteria will be randomized with an allocation ratio of 2:2:1:1 into 4 groups: QM 420 mg SC evolocumab + QD PO placebo, Q2W 140 mg SC evolocumab + QD PO placebo, QM SC placebo + QD 10 mg PO ezetimibe, Q2W SC placebo + QD 10 mg PO ezetimibe. Randomization will be stratified by screening LDL-C level and baseline statin use. Randomization should occur within 5-10 days of the screening LDL-C evaluation used to

determine eligibility. Subjects on low or atypical statin therapy must be on a stable dose for at least 4 weeks prior to the screening and throughout the blinded portion of the study; the dose cannot be adjusted during screening and for the duration of the study.

For blinding purposes, every subject will receive investigational product (IP) SC and PO. Patients will be provided with evolocumab or placebo through the use of an autoinjector (AI) or Personal Injector. Depending on availability either a single Personal Injector or 3 autoinjectors will be provided for monthly dosing. A single AI will be used for Q2W dosing. Evolocumab and corresponding placebo will be administered at the study site or at appropriate non-clinic setting per protocol Table 1 (Schedule of Assessment). PO placebo will be available to match PO ezetimibe through over-encapsulation. The SC IP dose frequencies of Q2W and QM will not be blinded.

Following the week 12 visit, all subjects will self-administer IP in the non-clinic setting; subjects will return to the clinical site at W24, W36, W48 and W52 for subsequent visits. There will be an end of study phone call at W54 (Q2W subjects only) for any potential adverse events, serious adverse events, or adverse device effects.

Central laboratory results of the lipid panel, ApoA1, ApoB, lipoprotein(a), and high sensitivity C-reactive protein (hsCRP) will be blinded during double-blind treatment. Investigators will be provided lipid results starting at week 24 until the end of study for each subject. All lipid results from posttreatment to week 24 will remain blinded until the unblinding of the clinical database.

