6.3 Other Study Related Definitions

Analytical Study Week Assignments

Analytical windows will be used to assign parameter measurements to study weeks.

The algorithm is provided in [Appendix B](#).

Actual Treatment Group

A subject's actual treatment group is the randomized treatment group, unless the subject receives treatment throughout the study that is different than the randomized treatment group assignment, in which case the actual treatment group is the treatment received.

Investigational Product (IP)

Blinded Period:

SC IP includes evolocumab SC 140 mg Q2W, evolocumab SC 420 mg QM and their corresponding SC placebo.

Oral IP includes ezetimibe PO 10 mg QD and placebo PO QD.

OLE: SC IP includes evolocumab SC 140 mg Q2W and evolocumab SC 420mg QM.

SC IP Exposure Period (Months) in Blinded Period

For each Q2W subject:

SC IP Exposure Period in Blinded Period = [min (EOS Date, the day before OLE day 1, Last SCBIPD + 14 days) - First SCBIPD + 1] / 365.25 * 12

For each QM subject:

SC IP Exposure Period in Blinded Period = [min (EOS Date, the day before OLE day 1, Last SCBIPD + 28 days) - First SCBIPD +1] / 365.25 * 12

Oral IP Exposure Period (Months) in Blinded Period

For each subject:

Oral IP Exposure Period = [min (EOS Date, the day before OLE day 1, Last POBIPD + 1 day) - First POBIPD + 1] / 365.25 * 12

SC IP Exposure Period (Months) in OLE

For each Q2W subject:

SC IP Exposure Period in OLE = [min (EOS date, last SCOLEIPD + 14 days) - First SCOLEIPD +1] / 365.25 * 12

For each QM subject:

SC IP Exposure Period in OLE = [min (EOS date, last SCOLEIPD + 28 days) - First SCOLEIPD +1] / 365.25 * 12

Study Exposure Period in Months

For each randomized subject:

Study Exposure Period = (EOS date – Randomization Date + 1) / 365.25 * 12

Treatment Emergent Adverse Event (TEAE)

Events categorized as Adverse Events (AEs) starting on or after first dose of investigational product as determined by the flag indicating if the adverse event started prior to the first dose of IP on the Events eCRF and up to 30 days after the last dose of IP date or EOS, whichever occurs first. Please see below for the definition of TEAE in blinded period and OLE.

TEAE	Summary period
Blinded period	Blinded period day 1 (the same as study day 1) through min(last dose date + 30 days, EOS date, the day before OLE day 1)
OLE	OLE day 1 through min(last dose date + 30 days, EOS date)

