10.6 Safety Analyses

10.6.1 Adverse Events

The Medical Dictionary for Regulatory Activities (MedDRA) version 20.1 or later will be used to code all events categorized as adverse events (AEs) to a system organ class and a preferred term. Severity of AEs will be graded using the CTCAE ([Appendix C](#)) and recorded on the eCRF. All adverse event tables will be summarized by actual treatment group. Treatment-emergent adverse events are events with an onset after the administration of the first dose of IP.

The subject incidence of AEs will be summarized for all TEAEs, serious TEAEs, TEAEs leading to withdrawal of investigational product, treatment-related TEAE and fatal TEAEs.

Subject incidence of all TEAEs, serious TEAEs, TEAEs leading to withdrawal of investigational product, and fatal TEAEs will be tabulated by system organ class and preferred term in descending order of frequency.

All TEAEs, serious TEAEs and TEAEs leading to withdrawal of investigational product will also be summarized by subgroups of age (< 65 years, ≥ 65 years; < 75 years, ≥ 75 years) and baseline statin use (Yes, No).

Subject incidence of TEAEs related to a device will be tabulated by preferred term in descending order of frequency.

Subject incidence of adverse events associated with injectable protein therapies:

- Injection site reactions
- Hypersensitivity or allergic reactions

will be summarized by category and preferred term. Neurocognitive events will also be summarized.

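### The protocol gives conflicting end dates for SAE collection, and the SAP's TEAE cut-off can leave collected serious or fatal events out of the safety tables

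*Protocol*

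**What the plan says.** **End of SAE collection.** The protocol gives three statements.

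- Section 9.2.2: "through 30 days after the last day of the dosing interval of investigational product(s) or end of study, whichever is later".
- Table 1, footnote a: "from signing of the ICF through 30 days post last dose of IP or EOS, whichever is later".
- Section 9.2.3: sites need not actively look for SAEs once the reporting period is over or once the study has ended. Any SAE they become aware of later still goes to the sponsor within 24 hours and into the safety database.

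The last scheduled adverse event review is the W52 visit for QM subjects and the W54 telephone call for Q2W subjects, who alone receive that call.

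**Tabulation.** SAP Section 6.3 counts an event as treatment-emergent "up to 30 days after the last dose of IP date or EOS, whichever occurs first". Its row for the open-label extension (OLE) applies the same minimum. SAP Section 10.6.1 restates the definition with no end date: "Treatment-emergent adverse events are events with an onset after the administration of the first dose of IP". It then plans tables of serious TEAEs and fatal TEAEs, and no table or listing of other serious or fatal events. Protocol Section 10.5.5 plans tables of fatal and of serious adverse events without restricting them to treatment-emergent ones. SAP Section 11 names only the dropped physical measurements as a departure from the protocol.

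**The concern.** Two things do not line up. First, a site reading Section 9.2.2 and a site reading Table 1 would close SAE collection on different days, and Section 9.2.3 can be read as allowing either to stop active follow-up at end of study. Second, the protocol collects to the later of two dates and the SAP tabulates to the earlier, so some events are reportable but have no planned table.

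Safety and tolerability is a secondary objective, and about 60 subjects are planned. With so few, one serious or fatal event missing from a table changes what the report shows.

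**Working it through.** **Inputs**

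- Visit days, SAP Appendix B (7 × week + 1): W48 = 337, W52 = 365, W54 = 379. All three reproduce.
- Dosing intervals, protocol glossary: Q2W 14 days, QM 28 days.
- Last QM dose: W48. Table 1 shows a dose there and none at W52, where only accountability is planned.
- Last Q2W dose: not stated in the readable text. W50 (7 × 50 + 1 = day 351) is inferred from two-weekly dosing with no W52 dose. W48 and W52 are shown as the range.
- Individual EOS, protocol glossary: the last protocol procedure, so W52 for QM and W54 for Q2W.

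**Formulas**

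- Section 9.2.2 end = max(last dose + interval + 30, EOS)
- Footnote a end = max(last dose + 30, EOS)
- SAP OLE window end = min(last dose + 30, EOS)
- Shortfall = collection end − last scheduled contact

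**Results for subjects dosed to the end of the schedule, at nominal days**

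| Case | Last dose | Last contact | 9.2.2 end | Footnote a end | 9.2.2 shortfall | Footnote a shortfall | SAP window end |
|---|---|---|---|---|---|---|---|
| QM, W48 | 337 | 365 | 337+28+30 = 395 | 337+30 = 367 | 30 | 2 | min(367, 365) = 365 |
| Q2W, W50 (assumed) | 351 | 379 | 351+14+30 = 395 | 351+30 = 381 | 16 | 2 | min(381, 379) = 379 |
| Q2W, if W48 | 337 | 379 | 337+14+30 = 381 | max(367, 379) = 379 | 2 | 0 | min(367, 379) = 367 |
| Q2W, if W52 | 365 | 379 | 365+14+30 = 409 | 365+30 = 395 | 30 | 16 | min(395, 379) = 379 |

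For QM the two protocol rules differ by 395 − 367 = 28 days; for Q2W with a W50 last dose, by 395 − 381 = 14 days. Counting the dose day as day 1 of the interval takes one day off each Section 9.2.2 end. Allowing for dose windows (± 7 days QM, ± 3 days Q2W) and the ± 3-day contact window, the Section 9.2.2 shortfall is 20 to 40 days for QM and 10 to 22 days for Q2W with a W50 last dose.

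**Days reportable under Section 9.2.2 but outside the SAP window:** QM 395 − 365 = 30; Q2W with W50 395 − 379 = 16 (W48: 381 − 367 = 14; W52: 409 − 379 = 30).

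**Subjects who stop IP but stay in the study.** Protocol Section 6.2.1.2 keeps a subject who cannot tolerate IP on the visit schedule to the end of the study. Take a QM subject whose last dose is at W24 (day 169). The SAP window closes on day 169 + 30 = 199. Adverse event reviews continue at W36 (day 253), W48 and W52 (day 365). That leaves 365 − 199 = 166 days in which SAEs are asked about and collected but are not TEAEs under SAP Section 6.3. This result depends neither on the last Q2W dose nor on which protocol rule is kept, since EOS is the later date under both.

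The blinded-period row in SAP Section 6.3 carries the same 30-day cap. A subject whose last blinded dose of any IP falls on day 29 (W4) leaves the window on day 59, which is 85 − 59 = 26 days before W12.

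**The case against.** A reader might infer that late SAEs are neither asked about nor tabulated. The documents do not support that reading.

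- **Reporting.** Section 9.2.2 covers whatever the investigator observes or the subject reports, with no need for a scheduled contact, and Section 9.2.3 requires later-discovered SAEs to be submitted. What is absent is a scheduled question, not the duty to report.
- **Contact.** Under footnote a the shortfall is 2 days for QM, and for Q2W with a W50 last dose. That is inside the ± 3-day window of the W52 visit and W54 call, so the schedule fits that rule. Only Section 9.2.2 gives 30 days for QM, and the 16 days for Q2W also depend on the W50 inference.
- **Tables.** Protocol Section 10.5.5 plans serious and fatal tables without a treatment-emergent limit and allows subject-level data when incidence is low. SAP Section 10.6.1 gives TEAEs no end date and could be read to include late events.
- **Principle and impact.** A site reporting window and a treatment-emergent window serve different purposes and need not coincide. SAP Section 6.3 records that the TEAE definition was documented before the primary-analysis unblinding. The end-of-schedule gap lies in the descriptive OLE, after the comparison with ezetimibe has ended.

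All of this stands, and it limits the point. It does not remove it. The protocol statements still differ. SAP Section 6.3 is the detailed TEAE rule, Section 10.6.1 names only serious and fatal TEAEs, and Section 11 declares no narrowing from the protocol. Different windows are legitimate, but then serious and fatal events outside the TEAE window need their own place in the outputs.

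**Conclusion.** A minor point, in two parts.

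1. **Protocol wording.** Section 9.2.2, Table 1 footnote a and Section 9.2.3 give different ends to SAE collection. For QM, Section 9.2.2 runs 30 days past the last scheduled contact and footnote a runs 2 days past it. For Q2W the Section 9.2.2 figure is 16 days, assuming a W50 last dose, with a range of 2 to 30 days. The passages must be reconciled; this review does not say which end date is right.
2. **Tabulation.** Serious or fatal events collected after EOS, or more than 30 days after the last dose in subjects who stop IP and stay on study, can be missing from the SAP tables. This part does not rest on the W50 assumption. It does rest on reading SAP Section 6.3 as governing over the open-ended sentence in Section 10.6.1.

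The documents do not support a claim that such events are lost to the sponsor, or that they certainly go untabulated. They leave the tabulation unsettled. The number of events affected cannot be estimated from the documents and is likely to be small.

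**What to change.** - **Protocol:** give one end date for SAE collection and use it in Section 9.2.2, Section 9.2.3 and Table 1 footnote a. If the chosen date falls after the last scheduled contact, state how the period between is covered; the SAP listing below does not close a contact gap.
- **SAP Sections 6.3 and 10.6.1:** use the same TEAE wording, including the end date, in both places. The definition documented before unblinding can stay as it is.
- **SAP Section 10.6.1:** add a table or listing of all collected serious and fatal events regardless of the TEAE cut-off, marking those outside the TEAE window. If limiting the tables to TEAEs is intended, record it in Section 11 as a change from Protocol Section 10.5.5.

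The cost is a protocol wording change, a few lines in the SAP and one output. The listing uses data already collected and needs no new procedure. SAP Section 10.1 already updates the OLE analyses from the final database lock, so the listing can be produced then.
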